6.3.1 Implant/Procedure

All participating subjects will undergo 3.0T MRI and CT scans to be used for surgical planning. The imaging protocol will consist of anatomical imaging using susceptibility-weighted imaging (SWI), T1-, and T2-weighted sequences. The brain MRI (Stealth Station, Medtronic) will be fused in stereotactic space, to the CT to determine the initial electrode trajectory to STN and confirm final electrode location.

Patients will undergo a preoperative stereotactic MRI as described above. On the morning of surgery, patients will undergo placement of the Leksell frame under local anesthesia, and will then undergo a stereotactic CT scan. Three simultaneous microelectrode recording tracks will be performed, with one electrode oriented along the CT/MRI-derived electrode trajectory, one 2-mm anterior, and one 2-mm lateral.

Single unit activity (SUA) and LFP recordings will begin at 20mm above the presumptive target and three microelectrodes will be advanced through the target to a position 3-mm below the intended target, in 1mm increments until 10mm above target. Then reduce increment to less than 0.5mm until the electrode reaches 3mm below the target. The positions of initial 3-microelectrodes will be modified if necessary due to the lack of excessive beta band activity. At each depth, microelectrodes will be used to record both LFP and SUA for 30 seconds.

The neurosurgeon will use standard clinical technique for localizing the STN, via real-time auditory and visual analysis of the SUA. The dorsal, ventral, and posterior borders of the STN will thus be identified, and STN neurons examined for movement-responsive receptive fields. The ventral border of the STN will be selected as the desired depth for the tip of the chronic DBS electrode. Our previous recordings indicate that STN can be identified with an excessive beta band activity of LFPs. Therefore, the optimal trajectory and electrode depth will be selected based on the excessive LFP activity and combination of SUA signal analysis.

Then the directional lead will be implanted and LFP signals will be recorded from all 8 contacts of the macroelectrode with 1-3-3-1 configuration. The LFP signal will be recorded from the target for 1min in resting and hand movement states (Aim-1). During these recordings, the neurologist who will test patient programming will be blinded to LFP data. Therefore, in each patient the optimal stimulation contacts will be selected without any influence from the LFP analysis.

The LFP recordings will be obtained using the gHamp biosignal amplifier (Gtec, Inc. Austria) at 2.4 kHz and 24 bit resolution. The depth information will be obtained from the Neurodrive (Alpha Omega, Nazareth, Israel), through a custom Ethernet based interface which was previously developed in [name] lab. Besides neural activity, we will record other biomedical and physiological signals with a variety of sensors, including a 2-channel bipolar electrocardiogram, 4 channel electromyogram (EMG; 2 upper and 2 lower limbs), and two 3-axis accelerometers attached to contra-lateral limbs. These signals will be entered into the multipurpose neural data acquisition system in order to synchronize behavior with the neural data. Resting and movement periods of the recording will be identified from the EMG and wireless 3-axis accelerometer sensors. The recorded data will be converted to Matlab (Mathworks, Natick MA) format, as described previously (Ince et al, 2010) for further analysis. The LFP data will be processed offline, using state-of-the-art signal processing and spectrum estimation techniques, to identify novel neuro-markers that will be used for the prediction of prediction of optimal stimulation contacts and correlation with the symptoms of the patient.

The efficacy of stimulation will be validated intraoperatively with concurrent testing of parkinsonian features and the absence of stimulation side-effects, per clinical routine. For instance, the presence of low-threshold side effects of stimulation, indicating electrode position too close to an adjacent structure—e.g., internal capsule or medial lemniscus or nucleus of cranial nerve III, when STN is the desired target—would require repositioning in order for the electrode to be clinically useful.

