Fig.1. The schematic diagram of our blinded study design is given in the top image. The LFP and SUA recording will be obtained in the OR and information obtained from both modalities will be used for track selection. Intraoperative LFP recordings will be obtained simultaneously with SUA from three trajectories identified by stereotactic imaging (A). The microelectrodes will be inserted towards the estimated target with a Neurodrive (B) to localize characteristic SUA or excessive LFP activity in the STN (D). After the identification of optimal track and depth, a directional DBS electrode (E) with 1-3-3-1 configuration will be implanted temporarily. LFP recordings will be obtained from all 8 contacts of the directional lead and will be processed in real-time intraoperatively with a system developed in [name] laboratory. The neurologist will be blinded to these LFP recordings (F). The therapeutic window will be studied with the implanted electrode by generation of the stimulation with 6 unidirectional and one omnidirectional pattern (G and E). The outcome of the unidirectional stimulation will be

4 Device(s) Under Investigation

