7.1.1.1 Analysis Methodology

To identify the location of the DBS electrode and its contacts as well as the directionality of the segmented contacts, the intra-operative and postoperative CT and 1.5T MRI scans will be merged in stereotactic space to the preoperative imaging dataset, using the Cranial Cloud interface.

Artifact-free LFP segments at each depth will be identified by visual inspection of sensor data and video recording, and, will be subjected to spectral analysis. Power spectra of the monopolar and bipolar LFP signals will be computed using a multi-taper method, due to its low variance (Thomson 1982). Following computation of the power spectra in each 30s time segment, the power in the θ - (3-7 Hz), α - (7-13 Hz), β - (13-32 Hz), γ - (48-100 Hz) and upper gamma (200-400Hz) bands will be computed. This will provide a feature matrix representing the sub-band power levels at different depths during resting state and changes during movement-related segments for each monopolar and bipolar contact.

We will explore the dynamic LFP spectrum arising from each depth individually and investigate whether the depths related to increased β - (13-32 Hz) band power and **other frequencies** can be a predictor for the borders of the STN and optimal contacts used for DBS.

We expect that abnormal brain activity will be characterized by a preferred correlation process, reflective of the structure of the local neural elements. Abnormalities in local neural elements or circuits may produce time series with distinct autocorrelation patterns, which can then be captured by autoregressive (AR) model parameters. In brief, the AR model represents the current observation by a linear combination of the past samples and a white-noise input (Hayes 2006). The data in each epoch are assumed to be stationary, as they originate from the same depth. Each epoch is analyzed with an AR model of order p . The model is,

$$x_t = a_1 x_{t-1} + \dots + a_p x_{t-p} + e_t, \quad (1)$$

where x is the output sequence, LFP data, $a_{1..p}$ are the model parameters representing the weights of past samples, and e_t is the white noise.

This method provides a great advantage over other techniques in describing the entire length of the data in each segment by a few "subject specific" model parameters, consequently resulting in a significant

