reduction in the dimensionality of the data analysis. At each contact, the model parameters will be estimated by using Burg's Algorithm. The optimal model order will be selected based on the evaluation of three different criteria—i.e., Akaike Information Criterion (AIC), final prediction error (FPE), and minimum description length (MDL), as described previously (Hayes 2006).

Once the AR model parameters have been estimated from the LFP data, these model parameters will be used along with subband powers as characteristic features for the prediction of STN location and stimulation settings. In addition, we will investigate whether the model parameters of different DBS contacts identified during rest and movement correlate with stimulation settings. We will explore different regression and classification techniques such as linear regression, linear discriminant analysis (LDA) and support vector machine (SVM) to estimate the predictive capability of the features extracted from LFP data. The estimation of the generalization capability of the developed models will be assessed by implementing a cross validation procedure with independent learning and testing sets. This will help to clarify the extent to which the stimulation correlates with actual LFP model parameters.

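### LFP is to be tested as a predictor of the STN borders, but the single-unit border call it is tested against is not shielded from LFP, and labelling of moved microelectrode positions is unspecified

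*Combined protocol and SAP*

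**What the plan says.** **The test.** Section 7.1.1.1 will explore whether depths with raised beta power, and other frequencies, "can be a predictor for the borders of the STN and optimal contacts used for DBS". Autoregressive parameters and sub-band powers then serve as "characteristic features for the prediction of STN location and stimulation settings".

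**The reference.** Section 6.3.1 states: "The neurosurgeon will use standard clinical technique for localizing the STN, via real-time auditory and visual analysis of the SUA". It continues: "The dorsal, ventral, and posterior borders of the STN will thus be identified". On this wording the border label is an SUA label.

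**LFP in the same mapping.** Section 6.3.1 also states: "The positions of initial 3-microelectrodes will be modified if necessary due to the lack of excessive beta band activity". Later in that section, "the optimal trajectory and electrode depth will be selected based on the excessive LFP activity and combination of SUA signal analysis". The Fig. 1 legend in Section 3 adds that "information obtained from both modalities will be used for track selection".

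**The ventral border.** Section 6.3.1 ties lead depth to one of the borders: "The ventral border of the STN will be selected as the desired depth for the tip of the chronic DBS electrode".

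**Blinding and retention.** Blinding to LFP is stated for the neurologist (Fig. 1 legend; Section 6.3.1) and for the programming practitioner (Section 6). None is stated for the neurosurgeon who reads the borders. LFP and SUA are both recorded at each depth for 30 seconds, and the only filter stated for the LFP analysis is freedom from artifact (Section 7.1.1.1).

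**The concern.** A reference standard should be set without knowledge of the predictor being tested. Here the person calling the SUA borders works in a mapping where beta activity must be known, because it decides whether electrodes are moved and helps to decide trajectory and depth. Nothing in the plan separates the SUA call from that knowledge. If a doubtful border is called with the LFP trace in view, the call can lean towards LFP, and the later comparison counts that as predictive success.

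A second route is selection. A position that is STN by SUA but lacks beta is a miss for LFP, and it is the kind of position the move rule gives up. If no SUA call is made there before the move, the position cannot be scored even though its signals are stored.

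The stake is interpretive. Section 1.5 gives part of the overall goal as investigating LFP analysis as a tool in the operating room, and Section 7.1.1.2 says the observations will feed a later protocol. Agreement that is partly an artefact of the mapping could be carried into that design.

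**Working it through.** The documents give no agreement, accuracy or effect-size figure for border prediction, so there is no planned figure to reproduce. The check is mainly a reading of the text.

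**Step 1: which decisions use which signal (Section 6.3.1; Fig. 1 legend)**

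| Decision | Signal stated |
|---|---|
| STN localization and dorsal, ventral and posterior borders | SUA |
| Moving the initial three microelectrodes | Lack of excessive beta (LFP) |
| Choice of track | LFP and SUA |
| Trajectory and electrode depth | LFP and SUA |
| Lead-tip depth | Ventral STN border |

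LFP is not written into the border label. The last two rows meet at one place: lead-tip depth is set at the ventral border, which is an SUA border, while depth is also said to rest on LFP with SUA. The two statements agree only if LFP has some part in fixing the ventral border or if depth can differ from that border. The text does not say which.

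**Step 2: is the border call protected from LFP?** No blinding is stated for the border reader. No order is stated between the SUA call, the viewing of LFP and any move. No statement says that an SUA call is made at every position.

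**Step 3: does the move rule by itself inflate agreement?** Let s be the share of true STN positions that show excessive beta. The documents do not give s, so it is assumed, with range 0.5 to 0.9. Allow one independent replacement attempt when beta is lacking.

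- All recorded positions kept and labelled: expected beta-positive positions are s + (1 − s)s = s(2 − s), and expected positions are 1 + (1 − s) = 2 − s. The ratio is s, so there is no inflation.
- Moved positions left out: the share is 1 − (1 − s)². For s = 0.5, 0.7 and 0.9 this gives 0.75, 0.91 and 0.99, against true values of 0.50, 0.70 and 0.90.

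The second line shows only that the answer turns on a rule the plan does not state. It is not an estimate of bias here. It concerns whether beta is present on a track, whereas the planned question is where along a track the border lies, and the plan does not say that moved positions are left out.

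**Step 4: scale.** 8 patients × 2 sides = 16 sides, and 16 × 3 = 48 initial tracks. How many are moved is not stated.

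**The case against.** The strongest reply is that the reference is SUA, as Section 6.3.1 says, and that the sentences combining LFP with SUA govern track, trajectory and depth, which are different decisions. This stands. A reader might infer that LFP is built into the border labels. The documents do not support that for the dorsal and posterior borders, and for the ventral border they are only ambiguous.

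A reader might also infer that positions where LFP fails are dropped. The documents do not say so. Both signals are recorded at each depth, lack of beta is known only after recording, and artifact is the only stated filter. The natural reading is that the recordings are kept, and Step 3 then shows no inflation from moving electrodes. What remains is that keeping the signals does not supply an SUA label, and does not blind a label made with LFP known.

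It might further be inferred that depths far above target would flatter the accuracy. The plan specifies no depth-by-depth scoring, so that does not follow.

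Finally, border prediction is neither an objective nor an endpoint (Sections 5.2 and 5.3). It is introduced as exploration in an 8-patient pilot. That also stands, and it limits the severity.

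**Conclusion.** The point holds as a minor one. Followed as written, the plan compares LFP with an SUA border call that is not blinded to LFP, made in a mapping that LFP helps to steer. Agreement may be inflated in two ways: by an SUA call made with LFP known, most clearly at the ventral border, and by selection if moved positions are left unlabelled or unanalysed. The direction is towards a more favourable result for LFP, but the size is unknown. With all positions kept and labelled, the move rule alone contributes nothing. The conclusion assumes that the absence of any stated blinding or ordering reflects the plan; the case report forms are under separate cover (Appendix E) and may already log a call at each position. Contact concordance, the primary endpoint, and the blinding of the programmer are not affected.

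**What to change.** - **Section 6.3.1:** for each microelectrode position, log the SUA-only STN call (entry and exit depth, or that no STN was found) before LFP is consulted for that position and before any move.
- **Section 7.1.1.1:** define the reference border as this SUA-only call. Include every recorded position, moved ones too. Report border error in mm per track, and show results for initial and modified positions separately.
- **Section 6.3.1:** reconcile the statement that lead-tip depth is set at the ventral border with the statement that depth rests on LFP and SUA. How tracks or depth are chosen need not change for this analysis.

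The cost is one logged entry per position and a few sentences of analysis text, since both signals are already recorded at each depth. The downsides are a brief logging step during surgery and a possibly less favourable border-prediction figure. If logging in the operating room is impractical, a later reading of the stored SUA by someone without access to LFP would serve as a fallback, although it would not be the surgeon's real-time call.

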1.4 Design

This is a feasibility study designed to evaluate the usefulness of intraoperative LFP recordings obtained from the implanted DBS lead to predict ideal stimulation parameters.

Additionally this study will compare the therapeutic window for stimulation delivered through directional and conventional leads and determine if the spatio-spectral LFP patterns correlate with the presence of stimulation side effects.

Approximately 8 subjects will be enrolled in this clinical investigation. The clinical investigation will be conducted at 2 centers in the USA.

Subjects participating in this clinical investigation will be monitored during DBS implant procedure and programming. The expected duration of enrollment is 8 months. The total duration of the clinical investigation is expected to be 1 year.

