5.3.1 Primary Endpoint

Concordance between LFP derived predictions and clinically optimized stimulation parameters

In this project we will establish the feasibility of recording LFP data intra-operatively from DBS electrode contacts using a multi-channel, high throughput data acquisition system and investigate if patterns in LFP can be used to select the optimal contacts for patient programming. Establishing the role of identifying and localizing LFP patterns intraoperatively can play an essential role in assisting the clinician who is programming the patient to select the optimal contact, especially when electrodes with multiple contacts (>8) are employed during DBS therapy. In this scenario, conventional techniques employing systematic contact evaluations in various combinations will be impractical due to time constraints.

The recently developed directional lead of SJM with 1-3-3-1 configuration offers the possibility of recording LFP activity from multiple directions. The primary utility of the segmented electrode is to steer the stimulation such that the side effects can be minimized. However, multiple contacts (n=8) on the electrode increase the programming complexity. In this project, we aim to determine in a blinded manner whether LFPs can guide programming. The outcomes of this pilot project will establish the scientific basis for whether LFPs recorded from a segmented electrode can be used for clinical decision making and to fine tune stimulation parameters.

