5.4.2 Exclusion Criteria

Subjects who meet any of the following exclusion criteria must be excluded from the clinical investigation:

- Subject is not a surgical candidate;
- In the Investigator's opinion the subject unable to tolerate multiple programming sessions within a single setting;

- Subject unable to comply with the follow-up schedule

6 Procedures

Approval from the Sponsor must be received prior to initiating study procedures.

Enrolled subjects (as defined in section 6.2) will undergo DBS implant with the Infinity device according to standard clinical practice. During implantation procedure LFP will be recorded from the DBS leads contacts together with additional biometric measurements. The efficacy of stimulation will be validated intraoperatively with concurrent testing of parkinsonian features and the absence of stimulation side-effects, per clinical routine.

We will quantify the relief of symptoms through steered stimulation by contrasting the UPDRS scores before and after DBS in the outpatient clinical settings according to procedures described in the PROGRESS study for both directional and omnidirectional stimulation, and for identification of the therapeutic window. All subjects will undergo rigorous rating-scale-based assessment of the severity of their neurologic symptoms “off” and “on” PD medications, using the practically defined off state (CAPSIT-PD). Programming will be performed by an experienced clinical practitioner who is blinded to the LFP recordings and their analysis.

Following completion of this study, patients care will continue according to the PROGRESS study.

The following sections provide a detailed description of procedures required by this CIP.

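### The primary concordance endpoint has no reference rate, so a match on lead level could reflect a preference common to all leads rather than patient-specific LFP information

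*Combined protocol and SAP*

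**What the plan says.** Sections 1.5.1 and 5.3.1 define the primary endpoint as "Concordance between LFP derived predictions and clinically optimized stimulation parameters".

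Section 6.3.1 describes placement. Three microelectrode tracks are recorded, and "At each depth, microelectrodes will be used to record both LFP and SUA for 30 seconds". The depth target is the same for every lead: "The ventral border of the STN will be selected as the desired depth for the tip of the chronic DBS electrode". On track and depth it says: "Therefore, the optimal trajectory and electrode depth will be selected based on the excessive LFP activity and combination of SUA signal analysis". The Fig. 1 legend in Section 3 agrees that "information obtained from both modalities will be used for track selection". The directional lead (8 contacts, layout 1-3-3-1) is then placed, and "The LFP signal will be recorded from the target for 1min in resting and hand movement states (Aim-1").

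The clinical choice is protected by blinding. Section 6 states: "Programming will be performed by an experienced clinical practitioner who is blinded to the LFP recordings and their analysis".

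Section 7.1.1.1 sets out spectral and autoregressive features, linear regression, LDA and SVM, and cross-validation with separate learning and testing sets. Section 7.3 gives a Type I error of 0.05. None of 5.3.1, 7.1, 7.1.1.1 or 7.3 defines a match. Nor do they give an expected agreement without LFP information, a simple competing rule, a permutation reference or a success threshold. Section 7 says that further detail may be held in a separate SAP; the document reviewed contains none.

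**The concern.** A match rate has meaning only against the rate that would occur without patient-specific LFP information. If contact choices were spread evenly, that would be 1/4 for level. One placement rule for all leads may make both the LFP peak and the clinical choice cluster on a level, and the even-spread figure then no longer applies.

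The safeguards in the plan address other problems. Blinding stops the programmer from following the LFP, but it does not remove a preference that both choices share. Cross-validation limits overfitting. A preference common to all leads is present in the learning and testing sets alike, so a model can score well by learning it.

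Sections 5.3.1 and 7.2 say that the pilot will supply the scientific basis for deciding whether LFPs can be used in clinical decisions, and 7.1.1.2 says that it will inform a later protocol. A reader told that, say, half the leads matched could not tell whether the LFP had added anything to naming the same level every time.

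**Working it through.** **No figure to reproduce.** The plan states no expected concordance, threshold or power; 7.1.1.2 declines a power calculation.

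**Inputs from the documents.** 8 patients with bilateral leads, so up to 16 leads (7.1.1.3). The 1-3-3-1 layout gives 4 levels, two of them with 3 segments (6.3.1). With no preference, chance agreement is 1/4 on level and 1/3 on segment within a segmented level.

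**Assumptions (not in the documents).** Each choice falls on its favoured level in a share m of leads, m = 0.5, 0.6 or 0.7. The other three levels share the remainder equally. LFP peak and clinical choice are independent within a lead, so there is no patient-specific link.

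**Agreement expected without a patient-specific link**

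- Same favoured level: m² + 3 × ((1 − m)/3)²
  - m = 0.5: 0.250 + 0.083 = 0.333
  - m = 0.6: 0.360 + 0.053 = 0.413
  - m = 0.7: 0.490 + 0.030 = 0.520
- Different favoured levels: 2m(1 − m)/3 + 2 × ((1 − m)/3)²
  - m = 0.5: 0.167 + 0.056 = 0.222
  - m = 0.6: 0.160 + 0.036 = 0.196
  - m = 0.7: 0.140 + 0.020 = 0.160

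The no-information rate can therefore lie above or below 0.25.

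**Cross-validated accuracy without a link.** Simulation with 8 patients and 2 leads each, where the second side copies the first with assumed probability 0.5, and both choices favour the same level:

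| m | LDA on one LFP power feature, leave one patient out | Always name the most common level in the other patients |
|---|---|---|
| no preference | 25% | 25% |
| 0.5 | 30% | 44% |
| 0.6 | 39% | 57% |
| 0.7 | 51% | 69% |

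Cross-validation leaves the LDA above 25% although the LFP carries no patient-specific information. The simple rule, which uses no LFP, does better still, so it is the useful comparator.

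**Precision.** 8 matches in 16 has an exact 95% interval of 25% to 75%; 12 in 16 has 48% to 93%. Both treat the 16 leads as independent, which is optimistic because each patient contributes two.

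**What a re-pairing reference could do.** LFP maps are re-paired with clinical contacts across patients within center, keeping each patient's two sides together. Section 1.4 says "The clinical investigation will be conducted at 2 centers in the USA". For centers of 4+4 there are 4! × 4! = 576 re-pairings; for 5+3, 720; for 6+2, 1,440. In the simulations:

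- With no link, it rejects in about 1% to 3% of trials at a nominal 5%, so it is conservative.
- If the clinical choice copies the LFP level in 50% of leads, power is about 32% to 71% over the scenarios tried. At 30% copying it is about 13% to 32%. The low ends are at m = 0.7 (4+4).
- If the favoured level varies between patients because lead depth varies, and LFP and clinical choice are otherwise unrelated, it rejects in 6%, 9% or 17% of trials at m = 0.5, 0.6 or 0.7 (4+4).

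**The case against.** The strongest objection is that the shared preference is only a possibility. No section reports one, and three places suggest that it could be weak. Section 3 says there is no consensus on the best site for the active electrode. Section 6.3.1 calls for repositioning when side effects appear at low thresholds, so final depth can depart from the common rule. Section 7.1.1.2 reports heterogeneous LFP patterns. This stands, and it is why the size is left open.

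Second, this is an exploratory pilot with no threshold and no power claim, and a baseline can be added at reporting. That bears on the importance of the point, but it does not supply the missing reference. The plan also relates LFP activity to symptoms, promises to explore mismatches (5.2.1) and merges CT and MRI to locate contacts (7.1.1.1). These help interpretation without giving a comparator.

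Three stronger readings are tempting and are not supported:

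- *LFP-guided placement makes the endpoint circular or inflates it.* Depth anchored on SUA alone could create the same preference, so the issue is not specific to LFP guidance. Agreement could also fall below 25%.
- *Directional concordance is compromised.* Nothing says that LFP sets lead rotation, and no harm to within-level direction is shown.
- *The predictor is the same recording that was used for placement.* Section 7.1.1.1 does mention 30-second segments by depth, which resembles the microelectrode recordings. It also builds its features per contact, and 6.3.1 ties Aim 1 to the one-minute lead recordings. The text is too ambiguous to carry that claim.

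**Conclusion.** The point holds in limited form. The primary endpoint has no reference rate, and all leads share one track-and-depth rule. A raw match rate or cross-validated accuracy alone therefore does not show patient-specific LFP information about level.

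Whether a shared level preference exists, and how large it is, cannot be determined from the documents. The 16% to 52% range rests on assumed concentrations and on independence of the two choices. The accuracy and power figures also rest on the assumed correlation between sides, and the power figures on the assumed copying probability and center split. The importance is minor: the gap limits what an exploratory result can mean and does not break a confirmatory test.

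**What to change.** In 7.1.1.1, add the following, all as descriptive results with intervals:

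1. Report level concordance and within-level directional concordance separately. Leads programmed on a ring contact or in ring mode contribute nothing to the directional part.
2. Leave out whole patients, both sides together, in cross-validation.
3. Show LFP accuracy on level beside a leave-one-patient-out rule that always names the most common level in the remaining patients. For direction, show the 1/3 chance rate.

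Optionally, add the within-center re-pairing reference and repeat the full cross-validation in each re-pairing for any trained model. If only one center takes part (5.1 mentions both a single center and two), re-pair across all 8 patients. State its limits: it is conservative at n = 8, its power is low and lowest where the shared preference is strongest, and it does not remove lead-depth differences between patients. The merged CT/MRI contact locations can describe those differences.

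The cost is a little more analysis, with no new patient, procedure or CRF field. The downside is that the LFP result may look less favourable beside the simple rule.
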